5.1 Analysis Populations

The following analysis population will be used to summarize the results from this study:

- **Enrolled Population:** All participants who were signed informed consent

and met the study eligibility criteria.

- **Safety Population:** All participants who were enrolled in the study and received at least a partial tablet of ibrexafungerp. No treated participants will be excluded from the safety population.
- **Pharmacokinetic Population:** All participants who receive ibrexafungerp and who have at least one quantifiable PK parameter.

Participants who are excluded from the analysis populations will be listed by participant and treatment.

5.2 Study Participants

5.2.1 Participant Disposition

The number and percentage of participants belongs to each analysis population as defined in [Section 5.1](#) will be summarized and listed for all enrolled participants.

Participant disposition will be summarized using the number of participants who were enrolled, the number and percent of participants who complete the study, the number and percent of participants who discontinue the study, and the reasons for discontinuation. The denominator of percentage will be the number of participants enrolled. Participant disposition and completion status will be listed for all enrolled participants.

5.2.2 Protocol Deviations

Protocol deviations will be determined with complying with all IRB-established procedures. Protocol deviations will be listed by participant and treatment for all enrolled participants.

5.2.3 Participant Eligibility

Eligibility status based upon meeting protocol entrance criteria will be listed for all enrolled participants.

5.3 Participant Demographics

Demographics will be summarized using the safety population. The demographics consist of age, gender, race, ethnicity, height, body weight, and body mass index [BMI]. Individual demographics for the safety population will be listed by participant.

5.4 Medical History

During screening, a complete medical history for the prior 1 year will be recorded for each participant. Medical history will include medical diagnoses, major surgical procedures, pregnancy, postpartum, and lactation history.

Medical condition and/or significant medical history will be coded using Medical Dictionary for Regulatory Activities (MedDRA) Version 26.1 or later and listed by reported term, System Organ Class (SOC), and Preferred Term (PT). The number and percentage of participants will be summarized by SOC and PT for Safety Population.

Medical/surgical history will be listed by participant in the safety population. Listing will be sorted by descending total of ATC level and alphabetically in lower level.

5.5 Prior and Concomitant Medications

All medications (including prescription and OTC medications) taken within 14 days before dosing (Day 1) with study medication throughout the study, and through poststudy visit will be coded using WHO Drug Enhanced Dictionary (September 2023 version B3). Prior Medication and Concomitant Medication are defined as below:

- Prior medications are defined as medications that stop prior to the first dose of study drug.
- Concomitant medications are defined as medications that start within the period starting from the beginning of the screening period to the end of study (Day 5), and with end date no earlier than the first dose of study drug.

Medications with missing or partially missing start or end dates will be handled per the conventions described in [Appendix B](#). If it cannot be determined whether a medication was a prior medication due to missing or partial medication start or end dates, the medication will be considered concomitant. Concomitant medications will be summarized by Anatomical Therapeutic Class (ATC) level 1, ATC level 2, and Preferred Term. Prior and concomitant medications will be listed for each participant by treatment, Preferred Term, reported term, ATC level 1, ATC level 2, including the start and end dates, prior/concomitant flag, whether it is ongoing, dose, unit, frequency, route of administration and indication. The prohibited concomitant medications will be listed and tabulated in the same way as concomitant medications. Listing will be sorted by descending total of ATC level and alphabetically in lower level.

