APPENDIX B. CONCOMITANT MEDICATIONS DATE IMPUTATION

CM Start Date	CM Stop Date	Algorithms
Known	Known	
If stop date < start date of study drug: PRIOR
 
If stop date \geq start date of study drug, and start date \leq end of study: CONCOMITANT
 
If stop date \geq start date of study drug and start date $>$ end of study: POSTTREATMENT

	Partial	
Impute stop date as the latest date possible (i.e., last day of month if day missing or Dec 31 if day and month are missing), then:
 
If stop date < start date of study drug: PRIOR
 
If stop date \geq start date of study drug, and start date \leq end of study: CONCOMITANT
 
If stop date \geq start date of study drug, and start date $>$ end of study: POSTTREATMENT

	Missing	
No PRIOR assignment if stop date is missing
 
If start date \leq end of study: CONCOMITANT
 
If start date $>$ end of study: POSTTREATMENT

Partial	Known	
Impute start date as the earliest date possible (i.e., first day of month if day missing or Jan 01 if day and month are missing), then:
 
If stop date < start date of study drug: PRIOR
 
If stop date \geq start date of study drug and start date \leq end of study: CONCOMITANT
 
If stop date \geq start date of study drug and start date $>$ end of study: POSTTREATMENT

	Partial	
Impute start date as the earliest date possible (i.e., first day of month if day missing or Jan 01 if day and month are missing) and impute stop date as the latest date possible (i.e., last day of month if day is missing or Dec 31 if day and month are missing), then:
 
If stop date < start date of study drug: PRIOR
 
If stop date \geq start date of study drug and start date \leq end of study: CONCOMITANT
 
If stop date \geq start date of study drug and start date $>$ end of study: POSTTREATMENT

	Missing	
No PRIOR assignment if stop date is missing
 
Impute start date as the earliest date possible (i.e., first day of month if day is missing or Jan 01 if day and month are missing), then:
 
If start date \leq end of study: CONCOMITANT
 
If start date $>$ end of study: POSTTREATMENT

CM Start Date	CM Stop Date	Algorithms

Missing	Known	No POSTTREATMENT assignment if start date is missing If stop date < start date of study drug: PRIOR If stop date \geq start date of study drug: CONCOMITANT

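### SAP 5.5 leaves a drug with a known start before screening and a known stop on or after the first dose neither prior nor concomitant, while Appendix B calls it concomitant.

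*SAP*

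**What the plan says.** SAP 5.5 gives two definitions. The first rests on the stop date alone: "Prior medications are defined as medications that stop prior to the first dose of study drug". The second has two conditions that must both hold. One concerns the start: concomitant drugs are "medications that start within the period starting from the beginning of the screening period to the end of study (Day 5"). The other concerns the stop, and 5.5 joins it to the first with these words: "and with end date no earlier than the first dose of study drug".

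The section then sends some records to the appendix: "Medications with missing or partially missing start or end dates will be handled per the conventions described in" Appendix B. It adds a default to concomitant, limited in the same way: "If it cannot be determined whether a medication was a prior medication due to missing or partial medication start or end dates".

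Appendix B nevertheless has a row for records where both dates are known. Its rule there is "If stop date \geq start date of study drug, and start date \leq end of study: CONCOMITANT". That rule has no lower limit on the start date.

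Two displays depend on the class. The medication listing in 5.5 carries a prior/concomitant flag. For prohibited drugs, 5.5 says: "The prohibited concomitant medications will be listed and tabulated in the same way as concomitant medications".

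Protocol 11.2 sets what is collected: every medication taken from 14 days before dosing through the post-study assessments, whatever its start date, with a stop date or a note that it continues.

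**The concern.** The two definitions in 5.5 do not cover every drug that can be in the database. A woman may start a drug before her screening visit, still be taking it when dosed, and stop it during the stay in the unit. That drug is not prior, because it did not stop before dosing. It is not concomitant, because it did not start inside the window. The flag then has no valid value.

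Appendix B gives a different answer for the same record, so two programmers could produce different concomitant-medication tables from one database. The prohibited-medication display is restricted to concomitant drugs and inherits the gap.

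These tables will be read alongside 5 to 10 individual PK profiles, with a decision to stop or continue after the first five women. Anyone looking for a co-medication behind an unusual profile would expect the table to include drugs present at dosing that began before screening.

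**Working it through.** The plan states no figure to reproduce, so the check compares the two rules. Dates are compared as whole days.

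**Inputs.** S is the start day, E the stop day and B the day screening begins. The first dose is on Day 1 and the study ends on Day 5. Protocol 11.7.1 lets screening occur up to about four weeks before dosing, or on the same day as the Day -1 procedures, so B can run from about Day -28 to Day -1.

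**Rules.**
- SAP 5.5: prior if E < 1; concomitant if B ≤ S ≤ 5 and E ≥ 1.
- Appendix B, both dates known: prior if E < 1; concomitant if E ≥ 1 and S ≤ 5.

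**Comparison for drugs started by Day 5.**

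| Record | SAP 5.5 | Appendix B |
|---|---|---|
| Known stop before first dose | prior | prior |
| Known start from B to Day 5, known stop on or after Day 1 | concomitant | concomitant |
| Known start before B, known stop on or after Day 1 | **neither** | **concomitant** |
| Known start before B, no stop date | to Appendix B, if read as a missing end date | concomitant |
| Partial or missing start, known stop on or after Day 1 | to Appendix B | concomitant |

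The rules conflict only in the third row (S < B and E ≥ 1). Medications are recorded only through the post-study visit, so a known stop in that row will in practice lie between Day 1 and Day 5.

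**How far the gap reaches.** It depends on when the woman was screened:
- B = Day -28: starts on Day -29 or earlier.
- B = Day -14 (an illustrative midpoint): starts on Day -15 or earlier.
- B = Day -1: starts on Day -2 or earlier.

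So a drug taken from Day -20 to Day 2 is concomitant in a woman screened on Day -28 and unclassified in one screened on Day -14.

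**A sign that the gap is unintended.** A drug stopped on Day 3 whose pre-screening start is known only by year goes to Appendix B and becomes concomitant. With its full start date recorded, the same drug falls under the 5.5 text and has no class. Better data give a worse result.

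**After the change.** With the lower limit B removed, the 5.5 condition becomes S ≤ 5 and E ≥ 1 (or continuing). That is Appendix B's condition, and every drug started by Day 5 is then either prior or concomitant.

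**The case against.** The strongest reply is that most long-running drugs are already covered. A drug still being taken on Day 5 will normally have no stop date. Appendix B sorts dates only as known, partial or missing, so an ongoing drug fits under missing. There the rule is "No PRIOR assignment if stop date is missing", and a start on or before end of study makes the drug concomitant. A reader might infer from 5.5 that every ongoing drug started before screening drops out of the tables. The documents do not support that. The drugs Protocol 11.2 foresees, those a participant cannot stop, are mostly of this ongoing kind. This part of the reply stands. What remains is that the 5.5 listing records ongoing status separately from the end date and nowhere says that ongoing counts as missing.

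A second reply is that prohibited drugs have other safeguards. Protocol 11.2 excludes Appendix C drugs from the approval route for medication that cannot be stopped. Eligibility is reviewed at screening and predose, and SAP 5.2.2 and 5.2.3 list deviations and eligibility status. A reader might infer that a prohibited drug could go unseen altogether. That is too strong, because it would remain on the eCRF and should appear in the deviation listing. The safeguards have limits: exclusion criterion 5 names strong CYP3A4 inducers, whereas Appendix C also covers inhibitors. They also do not correct the table.

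A third reply is that Appendix B already shows the intended rule and a programmer would follow it. If so, nothing is lost, but that programmer would be setting aside the definition 5.5 gives for complete dates.

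**Conclusion.** The inconsistency is real and narrow. For a drug with a fully known start before screening and a fully known stop on or after the first dose, SAP 5.5 gives no class and Appendix B gives concomitant. Neither the referral to Appendix B nor the default to concomitant reaches records with complete dates.

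The consequence is limited to the medication displays: possible omission from the concomitant and prohibited-concomitant tables, and no valid flag in the listing. The documents do not say how many such drugs to expect. One woman among the five at the interim analysis is 1/5 = 20% of that sample, but this is only her share of the sample and does not estimate impact. A reader might infer that the PK results are at risk. They are not: the class enters no PK parameter, milk-to-plasma ratio, infant dose or analysis population.

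The conclusion assumes that dates are compared by day, that stop dates after Day 5 are not normally collected, and that a drug recorded as continuing is handled as having a missing stop date. If programmers treated continuing drugs as outside the missing category, the gap would be wider, so the text should settle that point too.

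**What to change.** Make two edits in SAP 5.5 before database lock:

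1. Define concomitant as any medication started on or before end of study that had not stopped before the first dose, meaning it stopped on or after that dose or is recorded as continuing. State that there is no lower limit on the start date.
2. State that Appendix B's classification applies to all medications, including those with complete dates, and that a drug recorded as continuing is handled under the missing-stop rows.

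Appendix B also has a post-treatment class that 5.5 does not define. One clause could add it, although it should be empty in practice because collection ends with the post-study visit.

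The cost is a few sentences of text. No new data are needed, and no PK analysis or population definition changes.

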5.6 Treatment Exposure and Compliance

The details of Ibrexafungerp treatment exposure and compliance, including actual dose (2 tablets x 150 mg or other), date time of dose, whether first treatment administered (yes/no), whether second treatment administered (yes/no) and reason for adjusted or missed dose will be listed by participant in the safety population. Percentage of compliance, number and percentage of participants with missing treatment or adjusted treatment will be summarized. The compliance will be calculated as total actual drug administered (mg) / total planned drug to be administered (mg) *100.

5.7 Pharmacokinetic Analysis

5.7.1 Plasma and Breast milk Concentrations

In displays of plasma and breast milk concentration summary statistics (and in PK analyses), all plasma concentrations below the limit of quantification (BLQ) of the assay will be treated as “0” if they occur before the first measurable or after the last measurable concentration, and will be set as missing for data points in between two measurable concentrations. If a sample is missing or the value is not reportable and is between two measurable concentrations, the value at that time point will be left blank for the analysis and reported as either Not Reportable (NR) or No Sample (NS).

Individual participant plasma and breast milk ibrexafungerp concentrations, actual breast

milk and blood sampling dates and times, actual volume of breast milk collected at each time interval, actual dosing information (actual time and date of dosing, and actual dose taken) will be presented by participant in data listings.

Ibrexafungerp concentrations in plasma and in breast milk measured over time will be displayed graphically for individual participants and for all participants in the PK population and will be summarized descriptively based on nominal times. Linear and semi-log plots of geometric mean (SD) and individual ibrexafungerp concentration versus time profiles will be displayed. These linear and semi log plots will be generated separately for time restricting up to 24 hrs and for complete study duration (0-108 hrs). For geometric mean concentration-time profile plots, the nominal PK sampling time will be used, for individual concentration-time profile plots, the actual PK sampling time will be used.

The daily infant dosage (total drug present in milk and consumed by the infant per day) will be calculated as follows:

- Calculated Daily Infant Dosage (mg/day) = Σ (total drug concentration in each milk collection multiplied by the expressed milk volume in each milk collection)

The Milk Plasma Ratio (M/P) will be calculated. $M/P = AUC_{0-24} \text{ milk} / AUC_{0-24} \text{ plasma}$.

The calculation of Milk plasma ratio (M/P) should be based on AUC and on multiple time points over 24 hours and not just a single point in time.

Milk plasma ratio (M/P) = $AUC_{0-24} \text{ milk} / AUC_{0-24} \text{ plasma}$

The relative infant dose (the percent of the weight-adjusted maternal dosage consumed in breast milk over 24 hours) will be calculated:

- Calculated Relative Infant Dose = Infant Dosage (mg/kg/day)/Maternal Dosage (mg/kg/day) multiplied by 100

A table will be provided to include summary statistics on daily infant dosage, relative infant dose, and M/P based on AUC_{0-24} . A listing of infant dose will be provided by time-point.

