New curative approaches are needed, particularly involving agents with fungicidal activity (ie, that are able to kill the fungus) and activity against fluconazole-resistant strains, so that the causative yeasts can be eradicated. A new therapeutic approach with these characteristics would be expected to result in improved short-term and potentially long-term outcomes for this condition.

Ibrexafungerp is the first of the triterpenoid class of  $\beta$ -1,3-D glucan synthase inhibitors. It is a semi-synthetic derivative of the natural product enfumafungin with in vitro and in vivo activity against *Candida* species.

It has the same molecular target as the echinocandins but is structurally distinct and may interact differently at the target due to its activity against echinocandin-resistant strains.

Ibrexafungerp has fungicidal in vitro activity against *Candida* species similar to that observed with the echinocandins. By way of comparison, the azoles are fungistatic, with colony forming unit (CFU) counts that parallel the growth control arm.

In June 2021 the US Food and Drug Administration (FDA) approved Ibrexafungerp ([Brexafemme Label, 2021](#)) for treatment of Vulvovaginal candidiasis.

**Adult Pharmacokinetics Summary:** After oral, single-dose administration, peak plasma ibrexafungerp concentrations occur within approximately 4 to 6 hours post-dose. Plasma concentrations declined from  $C_{max}$  in an approximately monophasic decline, with a harmonic mean terminal half-life ( $t_{1/2}$ ) of ~20 hours. The mean  $AUC_{0-\infty}$  and  $C_{max}$  appeared, in general, to be dose proportional for doses from 10 mg to 1600 mg. Plasma exposures of ibrexafungerp were not altered in participants who were older than 65 years compared to younger participants or in female compared to male participants after single oral dose administration.

Ibrexafungerp elimination is primarily hepatic metabolism; and approximately 1 to 2% of the total dose is excreted by the kidney following administration of a single IV dose.

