## 7.2. Rationale for Trial

The primary purpose of this study is to determine whether ibrexafungerp is excreted in breast milk of lactating women, and if so, to characterize PK in breast milk and plasma; calculate the potential infant exposure if lactating women are treated with ibrexafungerp; and characterize the safety and tolerability in lactating women. Based on 24-hour half-life, it is expected that approximately 15% of ibrexafungerp remains after 72 hours, so the collection period of 0 through 108 hours is considered sufficient to characterize the PK parameters.

Vulvovaginal candidiasis (VVC) is a common genital infection in women caused by *Candida spp.*, primarily *C. albicans* and *C. glabrata*. Several studies have reported that 75% of

women experience at least one episode of VVC during their lifetime and 5 to 10% experience recurrent VVC (rVVC) ([Sobel, 2007](#)).

Based on FDA Lactation Study Guidance ([FDA Guidance, 2019](#)), this drug has expected use in women of reproductive age similar to the marketed drugs that are currently commonly used for the indication of VVC in reproductive aged women.

Consequently, evaluation of products for treatment of lactating women with VVC is of importance.

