### **8.2. Secondary Objectives**

- To calculate the potential infant exposure to ibrexafungerp if lactating women are treated with ibrexafungerp.
- To characterize the safety and tolerability of ibrexafungerp in lactating women.

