4.1 Overall Study Design

This is a Phase 1 study designed to determine whether the given oral dose of ibrexafungerp is excreted in breast milk, and if so, to characterize ibrexafungerp PK in the breast milk and plasma of lactating women.

Participants will receive a single day of twice daily (BID) 300-mg (2 x 150-mg) oral ibrexafungerp doses given 12 hours apart (Q12H). Participants will receive both doses on site. Participants will be admitted to the clinic on Day 1, and may be discharged on Day 5, after the 108-hour procedures are completed, at the discretion of the Investigator.

Participants who discontinued may be replaced at the discretion of the investigator and Sponsor to ensure that up to 10 evaluable participants complete the study. The flow chart of the study design is given in [Figure 1](#) and the Schedule of Assessments is provided in [Table 1](#).

Figure 1:: Study Design

[figure not shown]

Table 1 : Schedule of Assessments

Study Procedures	Screening ^a	Day 1					Day 2	Day 3	Day 4	Day 5 Post-study
		Predose ^b	0 hr	8 hr	12 hr	24 hr	36 hr	48 hr	72 hr	108 hr
Informed Consent	X									
Inclusion/Exclusion	X	X								
Physical Exam ^c	X	X								X
12-Lead ECG ^c	X									
Enrollment		X								
Demographics and Medical History prior 1 yr (including pregnancy, postpartum, and lactation history)	X									
Height and Weight ^d	X									X
Vital Signs (HR, BP) ^c	X	X		X		X				X
Vital Signs (RR, Temperature)	X	X								X
Safety laboratory testing ^e	X	X								X
HIV/Hepatitis Screen	X									
COVID, Alcohol, and Urine drug screen (standard at site) ^f	X	X								
Pregnancy Tests (serum)	X	X ⁱ								X
Standard Meals		X-----								X
Study Drug Administration ^g			X		X					
Blood Samples for Ibrexafungerp Concentration ^h			X-----							X
Breast Milk Samples for Ibrexafungerp Concentration ⁱ			X-----							X

Abbreviations: BP = blood pressure; HR = heart rate; RR = respiratory rate, PK = pharmacokinetic, ECG = electrocardiogram, and HIV = human immunodeficiency virus

^a Pre-study screening to determine eligibility may be performed within 4 weeks prior to dosing with study medication.

^bThe Day 1 predose examinations and assessments may be performed up to 12 hours predose.

^cDuring physical examination at screening and predose participants will also be asked about physical activity. Prior to ECG the participants must be in a semi-recumbent position for at least 10 minutes prior to having heart rate, blood pressure, and ECG performed.

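### The 24-hour Relative Infant Dose is sound as a Day 1 figure, but no summarised infant-dose endpoint covers the milk collected from 24 to 108 hours after this single-day course

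*SAP*

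**What the plan says.** The secondary objective in Protocol 8.2, repeated in SAP 2.2, is: "To calculate the potential infant exposure to ibrexafungerp if lactating women are treated with ibrexafungerp". SAP 3.2 names two endpoints for it, Daily Infant Dosage (mg/day) and Relative Infant Dose (%).

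SAP 5.7.1 computes the daily dosage as the sum of "total drug concentration in each milk collection multiplied by the expressed milk volume in each milk collection". No time limit is attached to the sum. It describes RID in words as "the percent of the weight-adjusted maternal dosage consumed in breast milk over 24 hours" and gives the formula "Calculated Relative Infant Dose = Infant Dosage (mg/kg/day)/Maternal Dosage (mg/kg/day) multiplied by 100". Protocol 15.4 and the Synopsis carry the same definitions.

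The regimen is 300 mg at 0 h and 300 mg at 12 h on one day (SAP 4.1). Milk is fully expressed over set intervals to 108 h after the first dose (SAP 4.5.1).

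The summary table in SAP 5.7.1 holds daily infant dosage, RID and the 0-24 h milk-to-plasma ratio. For later infant dose the provision is: "A listing of infant dose will be provided by time-point". SAP 3.1 and 5.7.2 separately plan milk AUC by collection period, milk AUC to the last measurable concentration and milk AUC to infinity, with descriptive statistics.

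**The concern.** A per-day infant dose over a per-day maternal dose describes exposure fully when the mother takes the drug every day. With linear kinetics, AUC over one day at steady state equals AUC to infinity from one day's doses, so the daily ratio is also the share of maternal dose that eventually reaches the infant. Protocol 7.1 reports approximate dose proportionality for single doses from 10 to 1600 mg.

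A single-day course breaks that equivalence. The denominator holds the mother's entire 600 mg, while the numerator closes at 24 h, only 12 h after the second dose. The protocol's own rationale expects drug to persist well beyond that: "it is expected that approximately 15% of ibrexafungerp remains after 72 hours".

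At stake is whether the summarised results answer the objective. A woman treated as in this study receives one course, and an infant who kept feeding would be exposed after Day 1 as well. No planned summary gives that quantity as a dose. The interim analysis (SAP 5.9) asks whether five participants suffice to address the objectives, so the same gap carries into that decision.

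**Working it through.** **The plan's own figure first.** Protocol 7.2 expects about 15% remaining at 72 h with a 24 h half-life. At that time dose 1 is 72 h old and dose 2 is 60 h old:

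- dose 1: 0.5^(72/24) = 12.5%
- dose 2: 0.5^(60/24) = 17.7%
- mean: 15.1%, which reproduces the stated figure.

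**Inputs from the documents.** Equal doses at 0 and 12 h (SAP 4.1); half-life about 20 h with a roughly monophasic decline, and peak at 4 to 6 h (Protocol 7.1); half-life 24 h (Protocol 7.2); milk collection to 108 h (SAP 4.5.1).

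**Assumptions not in the documents.** One compartment with first-order absorption, a constant milk-to-plasma ratio, and constant milk output per hour.

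**Formulas.** ke = ln 2 / half-life, and ka solves ln(ka/ke)/(ka − ke) = Tmax. For one dose, the fraction of total AUC accrued by time t is

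G(t) = [ke·ka/(ka − ke)] × [(1 − e^(−ke·t))/ke − (1 − e^(−ka·t))/ka].

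For two equal doses 12 h apart, F(t) = [G(t) + G(t − 12)]/2. With a constant ratio and constant output, infant dose over a window is proportional to the change in F.

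**One end of the range (half-life 20 h, Tmax 4 h).** ke = 0.0347, ka = 0.828.

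- F(24) = (0.5457 + 0.3114)/2 = 0.429
- F(108) = (0.9753 + 0.9625)/2 = 0.969
- share in 0-24 h of the 0-108 h total: 0.429/0.969 = 44%; ratio 2.26

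**Other end (half-life 24 h, Tmax 6 h).** ke = 0.0289, ka = 0.506.

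- F(24) = (0.4697 + 0.2502)/2 = 0.360
- F(108) = (0.9531 + 0.9337)/2 = 0.943
- share: 0.360/0.943 = 38%; ratio 2.62

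| Half-life (h) | Tmax (h) | F(24) | F(108) | 0-24 h share of 0-108 h | Ratio, 0-108 h to 0-24 h |
|---|---|---|---|---|---|
| 20 | 4 | 0.429 | 0.969 | 44% | 2.26 |
| 20 | 5 | 0.419 | 0.968 | 43% | 2.31 |
| 20 | 6 | 0.409 | 0.968 | 42% | 2.37 |
| 24 | 4 | 0.376 | 0.945 | 40% | 2.51 |
| 24 | 5 | 0.368 | 0.944 | 39% | 2.56 |
| 24 | 6 | 0.360 | 0.943 | 38% | 2.62 |

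So 56-62% of the drug reaching milk by 108 h arrives after 24 h. Maternal dose is 600 mg in both denominators, so the ratio of course RID to Day 1 RID equals the ratio of infant doses.

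**Sensitivity to absorption.** With instantaneous absorption, the 0-108 h to 0-24 h ratio is 2.14 (half-life 20 h) or 2.39 (24 h). The result does not hinge on the absorption model.

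**Day by day.** The 24-48 h dose is 75-89% of the 0-24 h dose, and a 12-36 h window is 9-17% above 0-24 h.

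**The case against.** Four points on the other side have force.

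1. RID is a daily measure by definition and is labelled as one. The 0-24 h window contains both doses and is the highest of the study days, and the best-placed 24 h window exceeds it by at most about 17%. A reader might infer that RID is biased or mislabelled. The documents do not support that, because nothing in them presents RID as a per-course figure. What stands is that the daily figure alone does not give exposure from the course.

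2. A reader might infer that milk after 24 h drops out of the summaries. It does not. Milk AUC for the collection periods is a primary endpoint, AUC to the last measurable concentration and to infinity are summarised, and milk concentrations are summarised and plotted to 108 h. But none of these is an infant dose: AUC leaves out milk volume, and a listing gives no total per participant and no summary across participants.

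3. The direction of the error depends on the window. The daily dosage sum covers every collection, so read literally it runs to 108 h, and the mg/day figure would then be too high by the same 2.3 to 2.6 times. That reading contradicts the mg/day unit and RID's own 24 hours. The shortfall arises once the 24-hour definition is applied. Either way the text needs an edit.

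4. The multipliers come from a model. Protocol 9.4.1 lists changes in milk supply among the risks of interrupting breastfeeding, and whether the drug enters milk at all is the primary question. Extrapolating to infinity gives 2.3 to 2.8 times, but no milk is collected after 108 h, so the range to 108 h is the one to use.

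The documents also set no RID threshold, so no particular misjudgement of the drug can be claimed.

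**Conclusion.** The point holds as a gap in the infant-dose summaries. Daily Infant Dosage and RID, read over 24 hours, are valid Day 1 figures. They hold about 38-44% of the drug expected in milk by 108 h, so infant dose per course over the collected period is about 2.3 to 2.6 times the 24-hour value. No summarised endpoint reports that larger quantity in mg, mg/kg or percent of maternal dose.

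The size rests on the protocol's half-life and Tmax and on the three assumptions listed in the working. The gap itself rests only on the wording. It can be repaired from data already planned, so it is a worthwhile improvement to the SAP and no threat to the trial.

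**What to change.** In SAP 3.2, SAP 5.7.1 and the infant-exposure summary table:

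- Restrict Daily Infant Dosage and RID to the post-dose collections from 0 to 24 h, and label both as Day 1.
- Add cumulative infant dose per course: the sum of concentration times volume over the post-dose collections from 0 to 108 h, in mg and in mg/kg, using the same infant weight as the Day 1 figure.
- Add course RID = cumulative infant dose (mg/kg) / total maternal dose actually taken (mg/kg) × 100.
- State conclusions on infant exposure, at the interim and at the end, on the Day 1 and course figures together.

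Rows for 12-36, 24-48 and 48-72 h are optional; all fall on existing collection boundaries.

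The cost is SAP wording and a few table rows. Concentrations, volumes and actual doses are already recorded, so no samples or participants are added. The course figure will look less favourable than the Day 1 figure.
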